9.0 Analysis Plan

9.1. Data Sources

Data will come from EHR records extracted by healthcare personnel and from research records of post-enrollment and follow-up assessments.

9.2 Subject Population Initial Analyses Descriptive statistics will be used to characterize the participants randomized to all the incentive conditions and these data will be compared with the characteristics of all patients who are listed on the Cigarette User Registry and also for just those on the Registry who do not participate in the research program. The data from these patients will be compared with the data from research participants to assess the representativeness of the sample enrolled in the study.

9.3 Planned Analysis

Primary Aim

- To determine the relations between treatment engagement financial incentive amounts offered and likelihood of patient engagement in smoking cessation treatment (defined as setting a TQD and completing the two phone counseling calls (Pre-quit + Week 4).

Primary analysis. The primary outcome measure will be patient engagement in smoking cessation treatment (defined as setting a TQD and the number of completed phone counseling contacts). We will determine the percentage of those in each incentive condition who engage in smoking cessation treatment. We will use logistic regression analyses to contrast the likelihood of engaging in any smoking treatment (vs none) for the three incentive conditions (0 incentive, \$100, and \$50), with the 0 incentive condition being the reference condition in the primary analysis. We will also examine incentive condition effects on the number of scheduled counseling visits completed (0-3 visits) via ordinal logistic regression.

Additional exploratory analyses related to the primary aim. In additional exploratory analyses, we will determine the percentage of all GHC patients who are contacted by the TCOS and offered the Treatment Engagement Incentive. We will separately determine the percentage of those in each incentive condition who agree to set a TQD. We will use logistic regression analyses to contrast the likelihood of engaging in smoking treatment for the three incentive conditions, with (as mentioned above) the 0 incentive condition being the reference condition in the primary analysis, followed by comparison of the \$100 and \$50 conditions both with the reference condition and with one another. The primary analyses will not use covariates. Follow-up analyses will use the patient's home clinic and the patient's TCOS as covariates. Furthermore, using logistic regression, we will examine the relation between incentive condition and use of pharmacotherapy as the outcome (with medication orders and pick-up entered in the EHR and/or billing data).

Exploratory Aims

- Conduct exploratory analyses on the effects of the different incentive engagement amounts on biochemically confirmed point-prevalence 6-month abstinence and determine whether incentive conditions affect abstinence via their effects on smoking treatment engagement (i.e., whether smoking treatment engagement mediates the relations between different engagement incentive conditions and 6-month smoking abstinence).

Analysis. Logistic regression will be used to determine whether the different incentive levels (\$0, \$100, \$50) produce effects on 6-month, biochemically confirmed point prevalence smoking

abstinence using the strategy described for Primary Aim. Dummy coding will be used to compare: 1) each positive incentive condition with the 0 incentive condition, and 2) the two positive incentive conditions will be compared with one another. The primary analyses will not use covariates. Secondary models will adjust for the patient's home clinic and the patient's TCOS as covariates, Gender, race, cigarettes smoked/day will be added as covariates in later analyses. Mediational analyses will be done using incentive condition as the independent variable, engagement data as mediators (attendance at the initial treatment contact, number of counseling contacts made, or use of smoking medication). The outcome variable will be smoking abstinence at 3 months (self-report only) and 6 months (biochemically confirmed self-report).

- To determine the incremental cost-effectiveness of the different financial engagement incentive amounts with regard to total program costs vs. usual care, net monetary benefit (NMB), cost per quit, and incremental cost-effectiveness ratios (ICERs), with the last determined with regard to cost of additional smoker engaged in treatment and each additional individual who quits smoking.

Analysis. Cost data will come from: healthcare system costs in terms of outreach communications, TCOS time (related to outreach and counseling efforts), implementation costs, incentive costs, and medication expenditures (including related physician screening when it occurs). We will use methods recommended by the US Panel on Cost-Effectiveness in Health and Medicine¹⁰ and consistent with our prior research. We will measure costs from a societal perspective using data on smoking cessation benefits from publicly available Medicare and Medicaid reimbursement rates. Cost estimates will be converted to a common year and QALYs will be computed, using a rate of 3% to discount future outcomes and costs to present value. We will also conduct probabilistic sensitivity analyses to account for uncertainty. We will determine net monetary benefit (NMB), cost per quit (using 6 month abstinence rates), and incremental cost-effectiveness ratios (ICERs)¹¹. The components of NMB will be the added costs of the various incentive levels and the monetized value of the QALYs added by the treatments. Total intervention and implementation costs (including outreach and added TCOS time for intervention, implementation, and incentives) will be compared to program costs of the usual care approach to tobacco use (the TCOS intervention program prior to the incentive study implementation).

- To determine the representativeness of smoking treatment reach and smoking abstinence outcomes generated by the various engagement incentive amounts with regard to different groups of smokers: e.g., those low in socio-economic status, priority populations, different racial and ethnic groups.

Analysis. We will extract data from the EHR to characterize the healthcare system population of patients who smoke with regard to such factors as: gender, race, ethnicity, insurance mix. Such person factors will be related to the likelihood that the patient: responds to TCOS outreach, agrees to accept smoking treatment (agrees to a TQD and completes a counseling call), completes up to 3 counseling calls, picks up smoking medications, and achieves long-term abstinence. Logistic regression will be used to examine the likelihood that different person factors are significantly related to the various outcomes under the different incentive levels.

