2.0 STUDY SUMMARY

2.1 Synopsis

Full Title	Randomized Test of Financial Incentives for Smoking Cessation Treatment Engagement Among A Healthcare System's Universal Primary Care Population
Short Title	[Financial Incentives for Smoking Cessation Treatment Engagement]
Protocol Number	[HS IRB 2020-0717]
ClinicalTrials.gov Identifier & Summary	[pending] [This study is being done to see if financial incentives increase the rate at which smokers engage in cessation treatment.]
Number of Site(s)	Approximately 6 clinical sites in the United States
Main Inclusion Criteria	
 • Adult members (patients) of participating healthcare system • Current smokers • English- or Spanish-speaking (able to complete questionnaires in English or Spanish over the phone)
Main Exclusion Criteria	
 • Prior participation in the study • Has a target quit smoking day within the past or next 30 days in the EHR • Medicare or non-BadgerCare Medicaid billable insurance
Objective(s)	
Primary Objective
 
 • To determine the relations between treatment engagement financial incentive amounts offered and likelihood of patient engagement in smoking cessation treatment (defined as setting a target quit day and completing phone counseling). 
Exploratory Objectives
 
 • Conduct exploratory analyses on the effects of different incentive engagement amounts on biochemically confirmed point-prevalence abstinence 6 months post-quit date, and determine whether incentive condition affects abstinence via effects on smoking treatment engagement (i.e., whether smoking treatment engagement mediates the relations between engagement incentive condition and 6-month smoking abstinence). • To determine the incremental cost-effectiveness of varying financial engagement incentives with regard to total program costs vs. usual care, net monetary benefit (NMB), cost per quit, and incremental cost-effectiveness ratios (ICERs), with the last determined with regard to cost of each additional smoker engaged in cessation treatment and each additional individual who quits smoking. • To determine the representativeness of smoking treatment reach and smoking abstinence effects of various engagement incentive amounts with regard to different groups of smokers: e.g., those low in socio-economic status, priority populations, different racial and ethnic groups.

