Study Design	This is a randomized, active placebo-controlled, trial of the effectiveness of financial incentives for adults smokers to engage tobacco treatment.
Study Intervention	Adults meeting Cigarette User Registry criteria who call or are contacted by their healthcare system to discuss tobacco use will be randomized to \$100, \$50, or \$0 incentive for

	participating in quit planning and quit counseling with a tobacco cessation specialist. Questionnaires will be completed at Week 1, Week 4, Month 3, and Month 6; exhaled breath CO measurements will confirm abstinence at 6 months.
Total Number of Subjects	A total of 540 subjects will be recruited from 6 primary care clinics of the participating healthcare system.
Study Population	Males and females aged 18 or above who are current cigarette smokers.
Statistical Methodology	An intention-to-treat analysis using logistic regression to contrast the likelihood of smoking treatment engagement/entry for the three incentive conditions.
Estimated Subject Duration	The duration of the study for each subject is approximately 28 weeks.
Estimated Enrollment Period & Study Duration	Study enrollment and follow-up will occur over 18 months with the total expected duration of the trial to be 48 months.

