4.2 Aims

Primary Aim

1. To determine the relations between treatment engagement financial incentive amounts offered and likelihood of patient engagement in smoking cessation treatment.
 - a. Primary outcome measure: Patient engagement in smoking cessation treatment (defined as setting a TQD and completing the two phone counseling calls).

Exploratory Aims

1. To determine the incremental cost-effectiveness of the different financial engagement incentive amounts with regard to total program costs vs. usual care, net monetary benefit (NMB), cost per quit, and incremental cost-effectiveness ratios (ICERs), with the last determined with regard to cost of additional smoker recruited and each additional individual who quits smoking.
2. To determine the representativeness of smoking treatment reach and smoking abstinence outcomes generated by the various engagement incentive amounts with regard to different groups of smokers: e.g., those low in socio-economic status, priority populations, different racial and ethnic groups.
3. Conduct exploratory analyses on the effects of the different incentive engagement amounts on biochemically confirmed point-prevalence 6-month abstinence, and determine whether incentive condition affects abstinence via effects on smoking treatment engagement (i.e., whether smoking treatment engagement mediates the relations between different engagement incentive conditions and 6-month smoking abstinence).

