9.4 Power

This study is powered to detect a 12 percentage point difference in treatment engagement rates (defined as setting a TQD and completing 2 treatment phone counseling contacts) as a function of incentive amount. We believe that this rate is both feasible and of public health significance. We anticipate that the 0 incentive condition will have an engagement rate of about 15%. Since the rate of smoking treatment engagement is generally only about 5-7% in studies where incentives are not used we believe a 15% rate is conservative. We anticipate increased engagement in the control condition, relative to these earlier studies, because we believe it will be increased by TCOS contact and the opportunity to set a quit date on the contact call. We believe that a 12 percentage point increase above the 15% rate (to 27%) would be of public health significance. A total of 180 participants per group are needed to have power of .80 with alpha = .05 in a two-tailed test. This would translate into a study N = 540 with 180/condition for the comparison of each positive incentive condition vs the control condition. We make no a priori prediction about whether the \$100 incentive condition will increase engagement relative to the \$50 condition, but we certainly believe it will increase engagement relative to the 0 incentive condition. . Therefore, we propose an overall N=540.

While engagement is the principal outcome of this research we nevertheless have determined the effect size (increment in percent abstinent) we would need to have adequate power to detect difference in abstinence rates, as well. We anticipate that the \$0 incentive condition will produce abstinence in 15% of those who contact the TCOS. With n=180/condition, we will have power=.80 to detect at least an 11 percentage point increase in abstinence above the 15% base rate in a 2-tailed test at alpha .05.

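### The primary logistic model in 9.3 is written for an undefined any-treatment outcome, not the quit-date-plus-two-calls outcome that the protocol defines and powers

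*Combined protocol and SAP*

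**What the plan says.** The primary outcome is worded in several ways.

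- **4.2 Aims**, primary outcome measure: "Patient engagement in smoking cessation treatment (defined as setting a TQD and completing the two phone counseling calls".
- **9.3, Primary Aim**: the same definition with the calls named, "defined as setting a TQD and completing the two phone counseling calls (Pre-quit + Week 4".
- **9.4 Power**: the trial is sized on "treatment engagement rates (defined as setting a TQD and completing 2 treatment phone counseling contacts) as a function of incentive amount".
- **9.3, Primary analysis**, first sentence: the outcome becomes "defined as setting a TQD and the number of completed phone counseling contacts", which is a count with no threshold.
- **9.3, Primary analysis**, model: "We will use logistic regression analyses to contrast the likelihood of engaging in any smoking treatment (vs none) for the three incentive conditions", with $0 as the reference. A separate ordinal model covers the number of visits completed, 0 to 3.
- **2.1 Synopsis**: the primary objective has "defined as setting a target quit day and completing phone counseling", with no number of calls. The methodology row describes "logistic regression to contrast the likelihood of smoking treatment engagement/entry for the three incentive conditions".
- **9.3, representativeness aim** (exploratory): one step is "agrees to accept smoking treatment (agrees to a TQD and completes a counseling call", that is, a TQD and a single call.

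**The concern.** The Primary analysis paragraph governs the main test, and its dependent variable is not the defined outcome. Any treatment could mean a TQD alone, one call of any kind, or medication alone, since section 5.0 describes the treatment as medication plus three calls. If a TQD were enough, nearly every consenter would be a success, because 6.2 has each of them set a quit date.

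Patients who start and do not follow through are a foreseeable group. Section 7.1 distinguishes initiation (TQD and first call) from follow-through (Week 4 call), and 4.1 pays half the incentive for each call. Initiation is therefore of interest, but it is not the stated primary outcome.

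Two things are at stake. The main test could be significant with two-call engagement unchanged, or null when two-call engagement rises. And an endpoint worded several ways can be chosen after the data are seen, so a reader could not tell which version was prespecified.

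**Working it through.** **1. Reproduce the plan's figure.** Inputs from 9.4: p1 = .15, p2 = .27, two-sided alpha .05, power .80, 180 per arm. The test compares two proportions with pooled variance and no continuity correction.

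n = [1.960·√(2·p̄·(1−p̄)) + 0.842·√(p1(1−p1) + p2(1−p2))]² / (p2−p1)²

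With p̄ = .21:
- √(2 × .21 × .79) = .576
- √(.1275 + .1971) = .570
- n = (1.129 + 0.480)² / .0144 = 179.7, so 180 per arm

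Power at 180 is Φ[(.12·√180 − 1.129)/.570] = Φ(.844) = .801. Section 9.4 is right for the outcome it names.

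**2. Power of the test as written.** The documents give no any-treatment rate, so the $0 rates below are assumptions. The effect is carried over in two ways: the same 12-point gain, or the same odds ratio, (.27/.73)/(.15/.85) = 2.096.

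| Assumed $0 any-treatment rate | Power, +12 points | Incentive rate at OR 2.096 | Power, OR 2.096 |
|---|---|---|---|
| 20% | .74 | 34.4% | .87 |
| 25% | .69 | 41.1% | .91 |
| 30% | .66 | 47.3% | .93 |
| 40% | .63 | 58.3% | .94 |
| 50% | .63 | 67.7% | .93 |

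Power may be below or above .80. It is simply not the figure that 9.4 computed.

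**3. How far the two tests can disagree.** Each patient is classed as no treatment, some treatment short of two calls, or two-call engaged. The $0 two-call rate is 15%, and the $0 any-treatment rate is assumed to be 30%, 40% or 50%. There are 180 patients per arm, the same test, and 200,000 simulated trials per scenario.

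| Scenario (incentive vs $0) | Test as written significant | Two-call test significant |
|---|---|---|
| (a) Any treatment +12 points, two-call stays 15% | 63–67% | 5% |
| (b) Two-call 15% to 27%, any treatment unchanged | 5% | 81% |
| (c) Two-call 15% to 27%, any treatment +6 points | 21–23% | 81% |

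Scenarios (a) and (b) are bounding cases. They show that the choice of endpoint alone can reverse the result, not that it is likely to.

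**4. Does another model cover the two-call outcome?** The ordinal model analyses 0 to 3 visits, does not single out the Pre-quit and Week 4 calls, and is introduced as an additional analysis. The exploratory paragraph of 9.3 repeats the logistic contrast without the word any, but does not define engagement either. No model is explicitly tied to the binary two-call outcome.

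**The case against.** The strongest reply is that this is shorthand. The formally labelled primary outcome (4.2), the aim directly above the disputed paragraph and the power section all say TQD plus two calls. The sentence just before the model uses the defined term, engagement, and the next paragraph refers back to the same contrast without the word any. On that reading, the phrase only means engaged versus not engaged. This is plausible, but the document does not confirm it: the contrast with none favours the literal reading, and the synopsis names no number of calls and describes the model as one of engagement or entry. The representativeness passage is weaker evidence, since it concerns an exploratory aim and does not restate the primary outcome.

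The objection to the illustrations is partly right. Two-call patients are a subset of treated patients. With a 30% any-treatment rate, scenario (b) needs the share of starters who complete both calls to rise from 15/30 = 50% to 27/30 = 90%. Scenario (a) needs it to fall to 15/42 = 36%. Because both calls are paid for, movement in the same direction is the more natural expectation. It is also fair to show any-treatment rates of 20% and 25%, given the low uptake described in section 3.0; they are in the first table.

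Last, 9.4 says two contacts without naming them, and three calls are offered. If any two of three was meant, the named-call outcome is stricter than the one powered. That needs one clarifying sentence in 9.4.

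**Conclusion.** The concern holds, and the text must be corrected before analysis. The outcome modelled in the Primary analysis paragraph is not the outcome defined in 4.2 and in the 9.3 aim and powered in 9.4. This conclusion comes from setting the passages side by side and needs no assumed rate.

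The size of the consequence does depend on assumptions. For $0 any-treatment rates of 20% to 50%, the test as written has power .63 to .74 for a 12-point gain and .87 to .94 at an odds ratio of 2.1, against .801 for the two-call outcome. The finding is therefore not that the trial is underpowered, but that the stated power does not apply to the stated test. In the bounding scenarios one test is significant in 63% to 81% of trials and the other in 5%.

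**What to change.** - In 9.3, Primary analysis, fit the primary logistic model to one binary outcome: TQD set, Pre-quit call completed and Week 4 call completed (yes/no). Delete the restatement of the primary outcome as a count.
- Define any treatment (which calls, and whether a TQD or medication alone counts). Label it and the 0-to-3 visit count, with its ordinal model, as secondary.
- Use the same outcome wording in the synopsis, 4.2 and 9.4. In 9.4, state that the 15% and 27% rates refer to the Pre-quit and Week 4 calls; if they were meant for any two of the three calls, revisit them.

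This is a change of wording. N stays at 540 (180 per arm, power .801), provided the 9.4 rates apply to the named calls and call completion is recorded for every patient analysed.

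### Section 9.3 leaves the deciding test for the primary aim unclear: an unranked ordinal test and a count-based outcome sit in the primary paragraph, against a binary endpoint elsewhere

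*Combined protocol and SAP*

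**What the plan says.** Section 9.3, under 'Primary analysis', first defines the outcome as a target quit date (TQD) together with how many counseling calls were completed. It then specifies a logistic regression of any treatment versus none across the three incentive conditions, and the clause naming $0 as the reference group calls this the primary analysis. The paragraph ends: "We will also examine incentive condition effects on the number of scheduled counseling visits completed (0-3 visits) via ordinal logistic regression". The exploratory label appears only in the next paragraph, which begins "In additional exploratory analyses, we will determine the percentage of all GHC patients who are contacted by the TCOS". No order of testing or multiplicity rule is given.

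Other sections describe one binary outcome:
- The 2.1 synopsis names only "An intention-to-treat analysis using logistic regression to contrast the likelihood of smoking treatment engagement/entry for the three incentive conditions".
- Section 4.2 gives a single primary outcome measure: a TQD plus both counseling calls. The aim as restated in 9.3 identifies these as the Pre-quit and Week 4 calls.
- Section 9.4 powers the trial on "treatment engagement rates (defined as setting a TQD and completing 2 treatment phone counseling contacts) as a function of incentive amount".

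Sections 4.1 and 7.1 tie the incentive to the Pre-quit and Week 4 calls. The Week 1 call is part of standard care and earns nothing.

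**The concern.** A second inferential test of the same hypothesis stands under the primary heading with no rank, and the outcome definition in that paragraph fits it. If one test reaches p<.05 and the other does not, 9.3 does not say in terms which one answers the primary aim.

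The two tests also measure different things. The ordinal scale counts the unpaid Week 1 call. A patient with Pre-quit and Week 1 calls scores 2 and fails the endpoint; a patient with Pre-quit and Week 4 calls also scores 2 and meets it. An incentive that moved patients from the first pattern to the second would not register on the ordinal scale. At stake are the clarity of the primary conclusion and some added type I error if the test can be chosen after the results are seen.

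**Working it through.** **1. The plan's own sample size.** Inputs from 9.4: "A total of 180 participants per group are needed to have power of .80 with alpha = .05 in a two-tailed test" and "We believe that a 12 percentage point increase above the 15% rate (to 27%) would be of public health significance". With p1 = .15, p2 = .27 and mean .21, the pooled-variance formula is

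n = [1.960·√(2·.21·.79) + 0.842·√(.15·.85 + .27·.73)]² / .12² = [1.129 + 0.480]² / .0144 ≈ 179.7, so 180 per arm.

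The stated figure is reproduced, with power .80. It belongs to the binary TQD-plus-two-calls endpoint, not to any-versus-none and not to the ordinal count.

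**2. Method for the rest.** Three-arm trials with 180 per arm were simulated. Binary tests are pooled z-tests. The ordinal test is the proportional-odds score test (tie-corrected Wilcoxon) on 0–3 calls. 'Any treatment' is taken as at least one call. The documents give no call distribution, so these control patterns are assumptions, in the order none / one call / Pre-quit + Week 4 / Pre-quit + Week 1 / all three:
- (.70, .09, .03, .06, .12)
- (.82, .02, .02, .01, .13)
- (.60, .15, .03, .10, .12)

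In each, two-call engagement is the third plus the fifth entry, which is .15.

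**3. No effect: chance that at least one test has p<.05.**

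| Binary test paired with the ordinal test | Correlation with ordinal | One contrast | Both arms vs $0 |
|---|---|---|---|
| Binary test alone | – | 5% | about 9% |
| Any vs none, as written in 9.3 | .96 to above .99 | 5.4–6.2% | 9.9–11.0% |
| TQD plus two calls, as powered in 9.4 | .69–.92 | 6.9–8.4% | 12.4–14.9% |

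Repeat runs move these figures by up to about 0.3 points. Four further assumed control patterns, with any-call rates from 20% to 60%, gave 5.5–7.2% and 7.2–8.8% per contrast for the two pairings.

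**4. A true 15% to 27% effect, starting from the first control pattern.**
- Incentive arm (.62, .05, .06, .06, .21): power .81 for two calls and .53 for ordinal. They disagree in 30% of trials; the ordinal test alone is significant in about 1%.
- Incentive arm (.58, .09, .04, .06, .23): power .81 and .77. They disagree in 15%; the ordinal test alone is significant in about 5.5%.

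**5. Sensitivity to the assumed pattern.** If the whole 12-point gain comes from patients who would otherwise have made some calls but not both paid ones, two-call power stays at .81 while ordinal power falls to .08–.12. If the incentive raises only partial attendance (any-call up 12 points, two-call engagement unchanged), the ordinal test is significant in 52% of trials and the two-call test in 5%.

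**The case against.** The strongest reply is that the plan, read as a whole, already has a lead test. Section 9.3 attaches the primary label to the logistic regression and introduces the ordinal model only as something also to be examined. Section 4.2 has one binary outcome, the synopsis names only logistic regression, and 9.4 powers only the binary endpoint. A reader might infer from the shared heading that the tests are co-primary, or that either may carry the primary claim. The documents do not support that: presenting the ordinal result as primary would contradict three other sections. This part of the reply stands.

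It does not remove the conflict, because the outcome definition in the operative paragraph includes a call count, and the ordinal model is the one that analyses a count.

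Two points on size also stand:
- Against the any-versus-none test actually written beside it, the ordinal test adds only about 0.4 to 1.2 points of error per contrast. The larger figures arise only against the two-call endpoint, so they partly reflect the mismatch of binary definitions.
- Most disagreement under the planned effect is the powered test succeeding while the ordinal fails. The favourable-choice case, ordinal alone significant, is about 1–6% of trials. Against any-versus-none it is larger, 16.5% and 10.6% in the same two patterns, again because of the definition.

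**Conclusion.** The concern holds as a conflict within the plan over the deciding test. The weight of the text favours a binary lead, but the primary paragraph of 9.3 contains an unranked ordinal test and an outcome definition that fits it.

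Free choice between the tests would raise the null error per contrast from 5% to about 5.4–6.2% with the binary test as written, or about 6.9–8.4% with the powered endpoint. Over both arms the figures are 9.9–11.0% and 12.4–14.9%, against about 9% for a binary test alone. That 9% comes from having two contrasts with $0, which is a separate matter. All of these rest on assumed call distributions, and disagreement under an effect depends strongly on which patients the incentive moves. The conflict itself does not depend on them; it can be read directly from 9.3, 4.2 and 9.4.

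**What to change.** Make three edits in section 9.3:

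1. State that the only primary test is the logistic regression of the binary outcome in 4.2 and 9.4: TQD set, and both the Pre-quit and Week 4 calls completed.
2. In the primary paragraph, replace both the call-count wording of the outcome and the any-versus-none wording of the logistic model with that definition. Without this edit, naming the 9.4 endpoint as primary would leave 9.3 contradicting itself.
3. Move the ordinal 0–3 visit model to the additional exploratory analyses, described as supportive and unable to replace the primary result.

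The ordinal analysis is still run, and 180 per arm with power .80 still stands. The cost is that the ordinal result can no longer be presented as primary. Keeping both tests as equals would cost more: with a Bonferroni split (.025 each), the two-call test has power .71 at 180 per arm and needs 218 per arm for .80.
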